5.1.3 MASKING

At the fitting visit, only the participant will be masked of the lens type, the investigator will know which type is fit to make changes to the lens at this visit if needed. Strongly adhesive stickers will be placed on the packages/foils to mask the participant to the lens brand. At both dispense visits, participants will be masked to the lens type dispensed. The study personnel will determine the lens order according to the randomization schedule and will over-labeled the lens packages/foils prior to dispense.

5.2 INVESTIGATIONAL SITES

5.2.1 NUMBER OF SITES

This study will be conducted at approximately 5 optometry practice sites within the United States and Canada.

5.2.2 INVESTIGATOR RECRUITMENT

[figure not shown]
The principal investigator at each site will be required to fulfil the following criteria:

- Is a licensed Optometrist with at least two years of contact lens fitting experience.
- Can demonstrate training in Good Clinical Practice (GCP).
- Accepts responsibility for the conduct of the study at their site.
- Has in-office email and document scanning capabilities.
- Will scan and send all study visit documents to CORE, ideally the same day* as the visit or at most within 2 days of the study visit.
- Is willing to follow the study protocol and to co-operate with the study monitors at CORE.
- * Study documents are required as soon as possible because this allows for timely data review, query and entry.

5.3 STUDY POPULATION

5.3.1 SAMPLE SIZE CALCULATION

The sample size calculation was based on a recent study comparing Biofinity sphere and Total30 sphere; the data for subjective responses for ease lens handling for lens removal when reflecting in a typical day, collected at the 1-month visits: standard deviation of 2.0 (0 - 10 scale) was transformed to a standard deviation of 20 for using a 0 - 100 scale for this study. 90% power is achieved with a minimum sample size of 44 participants.

Therefore, up to 48 participants will be dispensed with study products with the goal to complete at least 44.

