4 HYPOTHESIS

The null hypothesis is that there will be no difference for the primary outcome variable between Lens A compared to Lens B.

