5 MATERIALS AND METHODS

5.1 STUDY DESIGN

5.1.1 OVERALL DESIGN

This study will be conducted at several optometry practices in the US and Canada. This study is a prospective, bilateral eye, subjected-masked, randomized, 1-month cross-over, daily-wear design involving two different silicone hydrogel toric lens types. Each lens type will be worn bilaterally for approximately one month, during which participants record their subjective lens-wear experience on three different days. Additional measures will be collected during in-office study visits.

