5.3.2 NUMBER OF PARTICIPANTS

Participants will be recruited using site records and databases where consent for contact about research has been provided. There will also be general advertising materials (e.g. posters, social media posts) and all these, including email scripts, will be approved by the ethics review board. All initial individual-targeted recruitment activities, such as any direct mailing of recruitment scripts, will be conducted by practice staff that are not directly involved in conducting the research. This separation will reduce any undue influence of the optometrist-patient relationship. This process will also eliminate opportunity for the investigator to access personal health information before any consent for disclosure is provided by the potential participant.

It is anticipated that up to 60 potential participants may attend a Screening visit and at least 48 participants will be randomized and dispensed with study products, with a target of at least 44 completing the study. Each site will dispense study products to approximately 10 participants.

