12 STATISTICAL ANALYSIS AND DATA MANAGEMENT

12.1 STATISTICAL ANALYSIS

All data will be analyzed by CORE at the University of Waterloo. Unmasked data analysis will be conducted using Statistica 14.0, Statsoft or other suitable software. Descriptive statistics will be provided on demographic data (age, gender, refractive error distribution, etc.). Table 7 lists the primary and other outcome variables and anticipated statistical procedures.

Visual acuity results will be converted to LogMAR for analysis purposes.

Comparisons will be made between the study lenses for the variables measured at the 1-month visits. Additionally, the subjective ratings completed on days 7, 14 and 27 with each study lens will be compared. A binomial test will be used to analyze the results for the count data of subjective preferences and experience responses. Where relevant, the number of "no preference" responses will be evenly distributed to the two options on the basis they would be equally likely to choose either.

For assessments conducted for each eye separately, the right eye will be used for analysis. If a general difference is found (paired t-test / Wilcoxon matched pairs) between OD and OS, a comment will be provided.

Where appropriate, data may be presented as both mean or median and as counts by 'bucket' groups.

Additional analysis may be conducted.

Table 6: Statistical procedures

Variable	Analysis	Statistical test
	Comparison between study lenses	Freidman ANOVA
	and time points	Wilcoxon matched pairs test
	Comparison between study days	Freidman ANOVA
	and/or between contact lenses per	Wilcoxon matched pairs test
	time point.	RMANOVA
Demographics,	Descriptive stats	One or more: mean,
lens fit variables		median*, mode, standard
		deviation, minimum,
		maximum, frequency count

^{*} For non-parametric data only

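### Does the 90% power claim at 44 participants fail because section 5.3.1 omits the target difference, the significance level and the type of SD?

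*Combined protocol and SAP*

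**What the plan says.** Section 5.3.1 takes its variability from an earlier comparison of the spherical versions of the two lenses. The source is described as "the data for subjective responses for ease lens handling for lens removal when reflecting in a typical day, collected at the 1-month visits", and the "standard deviation of 2.0 (0 - 10 scale) was transformed to a standard deviation of 20" for the present 0–100 scale. It then concludes that "90% power is achieved with a minimum sample size of 44 participants", and that "up to 48 participants will be dispensed with study products with the goal to complete at least 44". Section 5.3.2 puts the recruitment figure slightly differently: "at least 48 participants will be randomized and dispensed with study products".

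Section 5.1.1 describes a "randomized, 1-month cross-over, daily-wear design involving two different silicone hydrogel toric lens types", so each participant rates both lenses. Section 4 sets the hypothesis: "The null hypothesis is that there will be no difference for the primary outcome variable between Lens A compared to Lens B". The lens-comparison tests visible in Table 6 of section 12.1 are within-participant, among them the "Wilcoxon matched pairs test". None of these sections gives a target difference, a significance level or a within-participant correlation.

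**The concern.** A power figure means little without the difference it refers to, and section 5.3.1 gives none. The SD is a second difficulty. The power of a paired comparison depends on the SD of each participant's lens difference. Section 5.3.1 attaches its SD to subjective responses, which is most naturally read as the spread of ratings. The two SDs coincide only when a participant's two ratings correlate at 0.5.

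If a rating SD had been put straight into a paired formula, the stated 90% would be too high for any correlation below 0.5 and too low above it. A non-significant result on ease of lens removal, the primary outcome, could then not be set against the difference the trial was built to detect. The 48 also appears as a ceiling in one section and a floor in the next.

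**Working it through.** **Inputs from the documents.** SD 20 (2.0 × 10), 44 completers and 90% power (section 5.3.1); cross-over (section 5.1.1); a no-difference null (section 4), which implies a two-sided test.

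**Assumed, because not stated.** Significance level 5%; paired t-test; equal rating SDs for the two lenses wherever a correlation is used.

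**Step 1: can 44 be reproduced?** Take 20 as the SD of paired differences and 10 points as the target. The noncentrality is (10/20) × √n, with n − 1 degrees of freedom.

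| n | Noncentrality | Power |
|---|---|---|
| 43 | 3.279 | 0.8931 |
| 44 | 3.317 | 0.9000 |
| 48 | 3.464 | 0.9240 |

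So 44 is the smallest n that reaches 90%. The normal approximation, (20 × (1.960 + 1.282)/10)² = 42.0, rounds up to 43; the t-distribution adds one. The target and the SD both come out as plain figures, and the calculation is the one a cross-over calls for.

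**Step 2: what if 20 is a rating SD?** The SD of differences is then 20 × √(2(1 − ρ)), with ρ the correlation between a participant's two ratings. At n = 44:

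| ρ | SD of differences | Power for 10 points | Difference detectable with 90% power |
|---|---|---|---|
| 0 | 28.28 | 63% | 14.1 |
| 0.3 | 23.66 | 78% | 11.8 |
| 0.4 | 21.91 | 84% | 11.0 |
| 0.5 | 20.00 | 90% | 10.0 |
| 0.6 | 17.89 | 95% | 8.9 |
| 0.7 | 15.49 | 99% | 7.7 |

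A shortfall against 10 points needs both conditions: 20 is a rating SD, and ρ is below 0.5. The documents establish neither.

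**Step 3: is there a rival design that also gives 44?** Treating the two sets of ratings as independent, with SD 20 and a 14-point target, gives power 0.894 at 43 per lens and 0.901 at 44 per lens. That also lands on 44, but only through an unpaired formula. With 14 points and ρ = 0 in a paired test, power at 44 is 0.894 and 45 are needed. Nothing in section 5.1.1 or Table 6 suggests that pairing was ignored, and 14 was found by working backwards from 44.

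**Step 4: the significance level.** With SD of differences 20 and n = 44, the difference detectable with 90% power is 10.0 points at two-sided 5%, 9.0 at one-sided 5% and 12.1 at two-sided 1%. Only the two-sided 5% convention gives a round target.

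**The case for a change.** The strongest case for a change is that inferring 10 points from 44 is itself back-solving. With no target stated, almost any n can be matched by some difference and formula, so the exact match in Step 1 is suggestive and not proof. The wording of section 5.3.1 leans towards ratings, and the sponsor could settle the question in a sentence or two from its own calculation. This concerns the primary outcome, so a reader may fairly expect to see the planned difference.

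Much of this stands. The 90% cannot be verified from the documents, and stating the three inputs would improve the text. What does not stand is the step from unverifiable to deficient. Section 5.3.1 never says outright that its SD is of ratings: it gives one SD, from a study comparing two lenses at their 1-month visits, and that is compatible with the SD of the comparison. The low power figures rest on conditions that nobody has shown to hold, and above ρ = 0.5 the trial is better powered than it claims. The loss in interpretation is also limited. The observed lens difference and a confidence interval for it can be read without the planning figure.

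**Conclusion.** The concern does not call for a change to the plan. Section 5.3.1 is incomplete as a record, but its figure of 44 is not shown to be wrong, and it is reproduced exactly by a paired two-sided 5% test for 10 points with 20 as the SD of differences. That match rests on an assumed target and significance level, so it supports the figure without confirming it.

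If 20 were instead a rating SD, power for 10 points would range from 63% at ρ = 0 to 99% at ρ = 0.7, with a shortfall only below 0.5. The earlier sphere-lens data that would settle this are not in the documents. Whatever the answer, the choice of test, the estimated difference and its precision follow from the data collected, so carrying out the plan as written leaves the primary conclusion sound.

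The difference between sections 5.3.1 and 5.3.2 over 48 is a slip of wording. Both give 48 dispensed and at least 44 completing, an allowance of 4/48, or 8.3%, for drop-out.

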5.3.2 NUMBER OF PARTICIPANTS

Participants will be recruited using site records and databases where consent for contact about research has been provided. There will also be general advertising materials (e.g. posters, social media posts) and all these, including email scripts, will be approved by the ethics review board. All initial individual-targeted recruitment activities, such as any direct mailing of recruitment scripts, will be conducted by practice staff that are not directly involved in conducting the research. This separation will reduce any undue influence of the optometrist-patient relationship. This process will also eliminate opportunity for the investigator to access personal health information before any consent for disclosure is provided by the potential participant.

It is anticipated that up to 60 potential participants may attend a Screening visit and at least 48 participants will be randomized and dispensed with study products, with a target of at least 44 completing the study. Each site will dispense study products to approximately 10 participants.

5.3.3 INCLUSION AND EXCLUSION CRITERIA

A person is eligible for inclusion in the study if he/she:

- 1. Is between 18 and 39 years of age (inclusive) and has full legal capacity to volunteer;
- 2. Has read and signed an information consent letter;
- 3. Self-reports having a full eye examination in the previous two years;

- 4. Anticipates being able to wear the study lenses for at least 8 hours a day, 6 days a week;
- 5. Is willing and able to follow instructions and maintain the appointment schedule;
- 6. Habitually wears of toric soft contact lenses binocularly.
 - a. No more than 1/3 of the participants should be wearing daily disposable soft toric lenses:
 - b. the remaining 2/3+ of the participants must be planned frequent replacement soft toric lens wearers as follows^:
 - i. TOTAL30 for Astigmatism: maximum of 3 (~10%) (no target percentage)
 - ii. Biofinity toric: maximum of 13 (~40%) (PLUS a target of minimum 10 (~30%))
 - iii. Air Optix for Astigmatism (inclusive of +Hydraglyde): maximum of 10 (~30%) (PLUS a target of minimum 7 (~20%))
 - iv. ULTRA for Astigmatism: maximum of 5 (~15%) (no target percentage)
 - v. Acuvue Vita for Astigmatism: maximum of 3 (~10%) (no target percentage)
 - vi. Acuvue Oasys for Astigmatism: maximum of 10 (~30%) (no target percentage)
 - vii. Other brands of frequent replacement: maximum of 7 (~20%) (no target percentage)
- 7. Has refractive astigmatism of at least -0.75DC but no more than -2.75DC in each eye that is correctable with a soft toric lens with a cylinder power of no greater than -2.25DC;
- 8. Is ammetropic and requires a spectacle spherical component of +8.00 to -10.00D inclusively;
- 9. Can be fit and achieve binocular distance vision of at least 20/32 Snellen with the available lens parameters (see Table 1).

A person will be excluded from the study if he/she:

- 1. Is participating in any concurrent clinical or research study;
- 2. Has any known active* ocular disease and/or infection that contraindicates contact lens wear;
- 3. Has a systemic condition that in the opinion of the investigator may affect a study outcome variable;
- 4. Is using any systemic or topical medications that in the opinion of the investigator may affect contact lens wear or a study outcome variable;
- 5. Has known sensitivity to the diagnostic sodium fluorescein used in the study;
- 6. Self-reports as pregnant, lactating or planning a pregnancy at the time of enrolment#;

7. Has undergone refractive error surgery or intraocular surgery.

^These recommended percentages are reasonable estimates of market shares in the U.S. Exceptions may be permitted after discussion with the study monitor or sponsor to target the anticipated habitual lens distribution across all sites.

*For the purposes of this study, active ocular disease is defined as infection or inflammation which requires therapeutic treatment. Mild (i.e. not considered clinically relevant) lid abnormalities (blepharitis, meibomian gland dysfunction, papillae), corneal and conjunctival staining and dry eye are not considered active ocular disease. Neovascularization and corneal scars are the result of previous hypoxia, infection or inflammation and are therefore not active.

*Pregnant and lactating women are not being excluded from the study due to safety concerns but due to fluctuations in refractive error, accommodation and/ or visual acuity that occur secondary to systemic hormonal changes and water retention. It has further been shown that pregnancy could impact tear production, which could impact dry eye symptoms. Such fluctuations could affect the secondary outcome data, thereby negatively affecting study data integrity.

5.4 STUDY MATERIALS

Sites will be provided (if needed) with a trial kit of Lens A and will source their own trial kit or order trial lenses in the required parameters of Lens B. The sites will use these trial kits/lenses to fit Lens A and Lens B lenses to determine the optimal lens power. The final lens prescription has to be tested on eye and commercial boxes of Lens A and B will be ordered through the site's normal commercial route (Lenses from the fitting sets will not be used for dispensing). In case, the same prescription is worn on both eyes, a single 6-pack will be ordered to be split between both eyes.

Reimbursement to practice sites for study product expenses will be provided by CooperVision, after CORE has reconciled the invoices and the product accountability and dispensing logs.

CORE will provide all sites with the study paperwork. This will include participant informed consent letters and study data collection forms, product accountability logs and the participant dispensing logs. CORE will train site personnel to complete the forms correctly and provide continued support to answer queries on correct form completion.

5.4.1 LENSES

Both, Lens A and Lens B are cleared by the United States Food and Drug Administration (FDA) and are commercially available in the U.S. and Canada.

The table below lists the contact lens details for Lens A and Lens B including the lens parameters available for this study.

Lens	Lens A (Biofinity toric)	Lens B (Total30 for Astigmatism)
Manufacturer	CooperVision	Alcon
Material	comfilcon A	lehfilcon A
FDA Class	Gro	oup 5
+8.00D to +6.50D (0.50D) Sphere power (D) +6.00D to -6.00D (0.25 steps) -6.50D to -10.00D (0.50D)		0D (0.25 steps)
Cylinder powers (DC)	-0.75, -1.25	, -1.75, -2.25
Axes (steps)	10° to 180° (10° steps)	10° to 180° (10° steps)
Base curve (mm)	8.7	8.6
Diameter (mm)	14.5	14 5

Table 1: Lens characteristics & parameter to be used

5.4.2 LENS CARE PRODUCTS

It is expected that participants will continue to use their habitual lens care products with the study lenses. This will avoid any potential incompatibility the participants may have with a new care product. Each participant will be compensated for them using their own lens care product for the approximately 2-month study period. Participants who habitually use a daily disposable lens or use a care regimen that is not suitable with the use of the study lenses, will be provided with OptiFree Puremoist with Hydraglyde (Alcon). The sites will source commercial bottles of this care product and reimbursement will be provided by CooperVision, after CORE has reconciled the invoices and the product accountability and dispensing logs.

5.4.3 OTHER PRODUCTS

Sodium fluorescein will be used to assess corneal and conjunctival staining.

5.4.4 REWETTING DROPS

Participants will not be encouraged to use rewetting drops; however, those who habitually used rewetting drops will be allowed to continue using their normal drops.

5.4.5 DISPOSING OF STUDY PRODUCTS

At the end of the study, all sites will return all unused products to CORE, unless otherwise directed. Worn lenses will be disposed of by participants and at the sites according to local regulations.

5.4.6 PRODUCT ACCOUNTABILITY

Accountability logs are completed to record all study products that were used for each participant, which includes products used during the visits and those dispensed to and returned by each participant.

5.5 SCHEDULED AND UNSCHEDULED VISITS

This study has a minimum of 4 scheduled study visits, including the screening visit. There is an option for repeated screening visit if needed.

A scheduled 1-month follow-up visit may only take place when the participant attends wearing the study lenses for at least two hours that day. If this is not the case and the participant is not experiencing any problems with the lenses, the appointment will be rescheduled, ideally within the visit window.

Visits that fall outside of the specified visit windows will be designated as protocol deviations and at the end of the study, the data collected during protocol deviations will be assessed for their suitability to be included in the analysis population.

Table 3 summarizes the scheduled study visits and study codes.

Table 2: Summary of visits

Visit code	Approximate Duration	Visit Description
0	2 hrs	Screening, Habitual baseline (collect in-office ratings for subjective experience, satisfaction and agreement questions) & Fitting of study lenses
0/R1, 0/R2	As needed	Repeat Visit 0 if needed
1-0	0.75 hr	Dispense Lens type #1 (0-28 days after Visit 0); collect in-office subjective ratings after 10 mins of lens insertion; provide at-home diaries
2-0	1.5 hr	1-month follow-up Lens type #1 (28-32 days after 1-0); review at-home diaries; collect in-office ratings for subjective experience, satisfaction and agreement questions for Lens type#1
		Dispense Lens type #2; collect in-office subjective ratings after 10 mins of lens insertion; & Provide at-home diaries
3-0 and exit	1.5 hr	1-month follow-up Lens type #2 (28-32 days after 2-0); review at-home diaries; collect in-office ratings for subjective experience, satisfaction and agreement questions for Lens type#2; collect preference ratings between Lens type#1 and Lens Type#2
		Exit forms & remuneration

Visits 1-0 (Dispense Lens type #1) and 2-0 (Dispense Lens type #2) will count as day 0 Lens type #1 and #2 will be either Lens A or B, as determined by the randomization table.

[figure not shown]
5.5.1 VISIT 0 SCREENING & FITTING VISIT

Informed consent shall be obtained in writing from the participant and the process shall be documented before any procedure specific to the clinical investigation is carried out.

Participants will be assigned a unique alpha-numeric study ID after they sign the consent documentation i.e. before their eligibility for the study has been confirmed. Each site will use a different letter preceding the participant ID number. For example, participant 01 at site P will be P01, and participant 01 at site L will be L01. Ineligible participants will be discontinued from the study.

The investigator will determine participant eligibility using the inclusion and exclusion criteria. The study procedures are outlined below:

[figure not shown]
- 1. The participant is expected to insert their habitual contact lenses at least 2 hours before attending the visit.
- 2. The participant will be required to read and sign an Informed Consent Form (Appendix 1) prior to enrollment. When the participant has signed the consent form, the participant will be considered enrolled in the study and will be assigned a study ID.
- 3. Participant demographics and medical history (age, sex, medical conditions, medications, allergies).
- 4. Contact lens history (habitual lens information and wearing habits).

10. The participant removes their habitual contact lenses.

15. The investigator will fit both study lenses (Lens A and Lens B) using trial lenses following to the manufacturers fitting guidelines.

16.

- 17. The investigator will confirm that the participant meets the eligibility specifications set out in the inclusion criteria and exclusion criteria and is eligible to continue in the study.
- 18. Schedule dispense visit (0-28 days after Visit 0) and order both study lens types in the final prescriptions (only lenses from commercial 6-pack boxes are used for dispensing) see section 5.4 for details.

